7. DELAY OR DISCONTINUATION OF STUDY INTERVENTION AND PARTICIPANT DISCONTINUATION/WITHDRAWAL

7.1. Criteria for Delay of Vaccine Administration

7.1.1. Individual Participant Criteria for Delay of Study Vaccination

Body temperature must be measured on dosing visits before vaccine administration (body temperature must be measured via the axillary route and any axillary reading of ≥ 37.8°C/≥ 100°F may be confirmed by a rectal measurement). The following events constitute criteria for delay of injection, and if any of these events occur at the time scheduled for dosing, the participant may receive the study injection at a later date within the time window specified in the SoA (Table 1), or the participant may be discontinued from dosing at the discretion of the investigator (Section 7.2):

- Acute moderate or severe infection with or without fever at the time of dosing
- Fever, defined as body temperature $\geq 38.0^{\circ}\text{C}/\geq 100.4^{\circ}\text{F}$ at the time of dosing

Participants with a minor illness without fever, as assessed by the investigator, can be vaccinated.

Participants with a fever of $\geq 38.0^{\circ}\text{C}/\geq 100.4^{\circ}\text{F}$ will be contacted within the time window acceptable for participation and re-evaluated for eligibility. If the investigator determines that the participant's health on the day of dosing temporarily precludes injection, the visit should be rescheduled within the allowed interval for that visit.

If a participant was exposed to a household contact (excluding school or other exposures) who tested positive for SARS-CoV-2 after the participant received the first dose, the administration of the second dose may be delayed to allow for at least 14 days between the positive test or the last day of symptoms (if present) of the household contact and Dose 2 as long as the participant remains asymptomatic.

If a participant tests positive for SARS-CoV-2 after having received Dose 1 but remains asymptomatic and the second dose is due before 14 days after the positive test, administration of the second dose may be delayed to allow for at least 14 days between the participant's positive test and Dose 2 as long as participant remains asymptomatic.

If a participant tests positive for SARS-CoV-2 after having received Dose 1 and develops symptoms of COVID-19, the participant may still receive a second dose, but the second dose should be delayed until approximately 90 days after diagnosis with COVID-19.

Protocol: mRNA-1273-P206, Original

If a participant takes a prohibited drug therapy, an injection could be delayed within the visit window based on the joint decision of the investigator and the CRO's medical monitor (Section 6.5.3).

7.2. Discontinuation of Study Vaccination

Participant's parent(s)/LAR(s) can choose to discontinue study injection (ie, refuse the second dose) for any reason, without prejudice to further treatment the participant may need to receive.

The investigator, in consultation with the Sponsor's medical monitor, may withhold or delay a participant from further injection under the following circumstances:

- The participant's parent(s)/LAR(s) withdraw consent.
- The participant develops, during the course of the study, symptoms or conditions listed in the exclusion criteria (Section 5.2).
- The participant experiences an AE (other than solicited reactogenicity) after injection that is considered by the investigator to be related to IP (Section 8.11.8) and is assessed as severe (Section 8.11.7).
- The participant experiences an AE or SAE that, in the judgment of the investigator, requires IP withdrawal due to its nature, severity, or required treatment, regardless of the causal relationship to vaccine.
- The participant experiences an AESI (Section 11.2).
- The participant experiences a clinically significant change in general condition that, in the judgment of the investigator, requires vaccine withdrawal.
- The participant experiences anaphylaxis (described in Section 8.11.4) clearly related to IP.
- The participant experiences a hypersensitivity reaction related to IP.

The reason(s) for withdrawal from further injection must be recorded in the eCRF.

If a participant takes a prohibited drug therapy, the investigator could withhold the second dose based on a joint decision of the investigator and the CRO's medical monitor (Section 6.5.3).

Every reasonable attempt should be made to follow up with participants for safety throughout the entire scheduled study period according to the SoA (Table 1), even if the participant does not receive the second dose or misses 1 or more visits. Unless the participant's parent(s)/LAR(s) withdraw consent, the participant is expected to remain in the study and complete all scheduled visits and assessments.

Protocol: mRNA-1273-P206, Original

7.3. Participant Discontinuation/Withdrawal From the Study

Participants who withdraw or are withdrawn from the study will not be replaced. A "withdrawal" from the study refers to a situation wherein a participant does not return for the final visit planned in the protocol.

The participant's parent(s)/LAR(s) can withdraw consent and withdraw the participant from the study at any time during the study, for any reason, without prejudice to further treatment the participant may need to receive. The investigator will request that the participant complete all study procedures pending at the time of withdrawal.

If participant's parent(s)/LAR(s) desires to withdraw the participant from the study because of an AE, the investigator will try to obtain agreement to follow up with the participant's parent(s)/LAR(s) until the event is considered resolved or stable and will then complete the end of the study eCRF.

Information related to the withdrawal will be documented in the eCRF. The investigator will document whether the decision to withdraw a participant from the study was made by the participant's parent(s)/LAR(s) or by the investigator, as well as which of the following possible reasons was the cause for withdrawal:

- AE (specify)
- SAE (specify)
- Death
- LTFU
- Physician decision (specify)
- Protocol deviation
- Study terminated by Sponsor
- Withdrawal of consent by participant's parent(s)/LAR(s)
- Other (specify)

Participants who are withdrawn from the study because of AEs (including AESIs and SAEs) must be clearly distinguished from participants who are withdrawn for other reasons. Investigators will follow up with parent(s)/LAR(s) of the participants who are withdrawn from the study as result of an SAE or AE until resolution of the event.

Protocol: mRNA-1273-P206, Original

Any parent(s)/LAR(s) who withdraws the participant from the study may request destruction of any samples taken and not tested. The investigator must document this in the study site study records and inform the Sponsor.

If the participant's parent(s)/LAR(s) withdraw consent for disclosure of future information, the Sponsor may retain and continue to use any data collected before such a withdrawal of consent (Section 11.1.10).

The Sponsor will continue to retain and use all research data that have already been collected for the study evaluation, unless the participant's parent(s)/LAR(s) have requested destruction of these samples. All biological samples that have already been collected may be retained and analyzed at a later date (or as permitted by local regulations).

Unblinding of still blinded participants based only on parental/LAR request and not related to a safety event or health concern will not be permitted, in order to protect the data integrity of the blinded portion of the study. If a parent/LAR wishes to withdraw their child from the study, they may withdraw at any time but will only be able to learn the treatment group assignment once an unblinding trigger is reached as described in Section 6.3.8. If an unblinding trigger is reached and a participant who received placebo in the study chooses to receive a nonstudy COVID-19 vaccine, they will be withdrawn from the study (Section 6.3.8).

7.3.1. End-of-study Visit (Prior to Day 422)

Once the parent(s)/LAR(s) withdraw the participant from the study, the investigator (or delegate) should confirm all ongoing AEs have been addressed and answer any additional questions the participant's parent(s)/LAR(s) may have; this may be done via a telephone call. The communication should be documented in the source. The End-of-Study/Study Discontinuation eCRF page must be completed.

7.4. Study Pause Rules

The investigators, study medical monitor, and Sponsor will monitor for events that could trigger a study pause. Study pause rule criteria, events, and thresholds are described in Table 4.

Protocol: mRNA-1273-P206, Original

Table 4: Pause Rule Criteria, Events, and Thresholds

Pause Rule Criterion	Event	Participant Threshold for Triggering Study Pause				
Pause Rule Assessed by Investigator						
1	Any SAE that cannot be reasonably attributed to a cause other than the study vaccination	≥1				
Pause Rules to be Assessed by Medical Monitoring Team (Sponsor/CRO)						
2ª	Individual Grade 3 or higher solicited local AR lasting ≥ 24 hours in duration and occurring within 7 days of injection (Days 1 to 7) ^b	At least 2 participants and ≥ 5% of the dosed participants in each arm				
3ª	Individual Grade 3 or higher solicited systemic AR lasting ≥ 24 hours in duration that cannot be reasonably attributed to a cause other than the study vaccination, within 7 days of injection (Days 1 to 7) ^b	At least 2 participants and ≥ 5% of the enrolled participants in each arm				
4	Any severe unsolicited AE that cannot be reasonably attributed to a cause other than the study vaccination, within the 7-day (Days 1 to 7) post-vaccination period	At least 2 participants and ≥ 5% of the enrolled participants in each arm				

Abbreviations: AE = adverse event; AR = adverse reaction; CRO = contract research organization; eDiary = electronic diary; SAE = serious adverse event.

If any of the thresholds for a study pause are met, the Sponsor will immediately suspend further enrollment and/or study dosing by notifying all investigators and the DSMB will convene on an ad hoc basis. The DSMB will review all available unblinded study data (as applicable) to help adjudicate any potential study pauses and make recommendations on further study conduct, including requesting additional information, recommending stopping the study, recommending changes to study conduct and/or the protocol, or recommending additional operational considerations due to safety issues that arise during the study.

The investigator or designee is responsible for reporting each event that potentially meets any pause rule criterion within 24 hours of observation to the Sponsor. The Sponsor will inform the DSMB of any event that potentially meets the pause rule criterion. The DSMB will review all

^{a.} "Individual AR" is defined as 1 AR type, eg, pain, erythema, or headache could each be an "individual AR."

b. This will be tracked in the following manner: if a participant reports a Grade 3 or higher AR in 2 consecutive eDiary entries within 22 to ≥ 24 hours apart, the participant will be contacted and asked whether the AR lasted ≥ 24 hours in duration. If an eDiary entry is not entered the day after a Grade 3 or higher AR was reported, the participant will also be contacted and asked whether the AR lasted ≥ 24 hours in duration.

Protocol: mRNA-1273-P206, Original

available study data to help adjudicate such events in accordance with the DSMB charter (Section 8.12.2).

The Sponsor will notify the Center for Biologics and Evaluation Research within 48 hours in the event of a study pause. In the event of a study pause, all safety and immunogenicity assessments will continue per protocol. The window allowance for injection visits may be extended by an additional 7 days (ie, + 21 days) for affected participants at the discretion of the Sponsor.

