8.10.2. Use of Electronic Diaries

At the time of consent, participants' parent(s)/LAR(s) must confirm they will be willing to complete an eDiary using either an application downloaded to their smartphone or using a device that is provided at the time of enrollment. Before enrollment on Day 1, participants' parent(s)/LAR(s) will be instructed to download the eDiary application or will be provided an eDiary device to record solicited ARs (Section 8.11.3) on Day 1. Based on availability, smartphone devices may be provided to those participants' parent(s)/LAR(s) who do not have their own device to use for eDiary activities.

At each injection visit, participants' parent(s)/LAR(s) will be instructed (Day 1) or reminded (Day 57) on thermometer (axillary and rectal) usage to measure body temperature, ruler usage to measure injection site erythema and swelling/induration (hardness), and assessment for localized axillary swelling or tenderness on the same side as the injection arm/thigh.

At each injection visit, participants' parent(s)/LAR(s) will record data into the eDiary starting approximately 30 minutes after injection under the supervision of the study site staff to ensure successful entry of assessments. The study site staff will perform any retraining as necessary. Participants' parent(s)/LAR(s) will continue to record data in the eDiary after they leave the study site, preferably in the evening and at the same time each day, on the day of injection and for 6 days following injection.

Participants' parent(s)/LAR(s) will record the following data in the eDiary:

Solicited local and systemic reactogenicity ARs, as defined in Section 8.11.3, that occur
on the day of each vaccine administration and during the 7 days after vaccine
administration (ie, the day of injection and 6 subsequent days). Capturing details of ARs
in the eDiary should not exceed 7 days after each vaccination. If a solicited local or

Protocol: mRNA-1273-P206, Original

systemic AR continues beyond Day 7 after vaccination, the event should be reviewed by the study site staff either via a telemedicine visit/call or at an unscheduled study site visit.

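### Table 4 footnote b does not prompt the 24-hour duration question when Grade 3+ reactions are entered on two consecutive days less than 22 hours apart, although pause rules 2 and 3 turn on that duration

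*Protocol*

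**What the plan says.** Protocol 7.4, Table 4 gives rule 2 as "Individual Grade 3 or higher solicited local AR lasting ≥ 24 hours in duration and occurring within 7 days of injection". Rule 3 is the systemic counterpart: "Individual Grade 3 or higher solicited systemic AR lasting ≥ 24 hours in duration that cannot be reasonably attributed to a cause other than the" vaccination. Both are assigned to the Sponsor/CRO medical monitoring team. The threshold for rule 2 is "At least 2 participants and ≥ 5% of the dosed participants in each arm"; rule 3 uses the same numbers with enrolled participants as the denominator.

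Footnote b, attached to both rules, sets out how the 24-hour element is tracked. It has two prompts for contacting the family:

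- Prompt 1: "if a participant reports a Grade 3 or higher AR in 2 consecutive eDiary entries within 22 to ≥ 24 hours apart".
- Prompt 2: "If an eDiary entry is not entered the day after a Grade 3 or higher AR was reported, the participant will also be contacted".

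Protocol 8.10.2 says when entries are made: "preferably in the evening and at the same time each day, on the day of injection and for 6 days following injection". The fixed time is a preference. For temperature, the same section asks for the highest reading of the day only.

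**The concern.** Footnote b is meant to establish how long a Grade 3+ reaction lasted, but prompt 1 filters on the clock interval between two diary entries. The two are different quantities. The diary is completed once a day, and the hour at which a parent completes it says nothing about when the reaction began or ended. A reaction can run well past 24 hours while its two entries are 21 hours apart.

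The result is uneven. A parent who skips the entry after a Grade 3 report is called. A parent who confirms Grade 3 again the next day, 21.5 hours later, is not called under the footnote.

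What is at stake is timely recognition that a pause threshold has been met. While an arm is small, two infants are enough, so one unasked parent can leave the rule apparently unmet until someone raises the question by another route.

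**Working it through.** The plan states no error rate or detection probability for this rule, so there is no figure to reproduce. The check applies the footnote to example intervals, finds where a single case is decisive, and illustrates how often the gap could open.

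**Step 1: the two prompts applied to consecutive-day Grade 3+ entries.** Both entries are present, so prompt 2 never applies.

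| Interval between entries (h) | Second entry earlier in the day by (h) | Prompt 1 |
|---|---|---|
| 24 | 0 | yes |
| 23 | 1 | yes |
| 22.5 | 1.5 | yes |
| 22 | 2 | yes |
| 21.5 | 2.5 | no |
| 21 | 3 | no |
| 20 | 4 | no |

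For example, entries at 20:00 and at 17:30 the next day are 21.5 h apart and meet neither prompt. The gap opens only when the second entry is more than 2 h earlier. As a range, the wording of prompt 1 is also malformed: its upper end is itself a lower bound, so only the 22 h limit has any effect.

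**Step 2: where one case is decisive.** The number of cases needed is the larger of 2 and 5% of the arm, rounded up.

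- Two cases suffice while 0.05 × n ≤ 2, that is, n ≤ 40.
- n = 25: 2. n = 50: 3. n = 300: 15.
- SAP Section 7 reports 18 participants in Part 1 Arm 2 before the enrollment pause. There 5% is 0.9, so the threshold is 2.

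**Step 3: illustrative frequency.** Assumption, not from the documents: entry times vary independently and normally around a usual time, with standard deviation s hours. The interval between consecutive daily entries is then Normal(24, s√2), and

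P(interval < 22 h) = Φ(−2 / (s√2)).

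For two-day reactions with exactly two qualifying cases, the chance that at least one is not prompted is 1 − (1 − p)². For Grade 3+ on three consecutive days, both intervals must be under 22 h. These share the middle entry, so that probability was simulated (200,000 draws).

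| s (h) | One pair under 22 h (p) | At least one of two not prompted | Three-day reaction not prompted |
|---|---|---|---|
| 0.5 | 0.2% | 0.5% | about 0% |
| 1 | 7.9% | 15% | 0.04% |
| 1.5 | 17.3% | 32% | 0.5% |
| 2 | 24.0% | 42% | 1.6% |

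The exposure is therefore almost entirely in reactions at Grade 3+ on exactly two diary days.

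**Step 4: when another contact would find the case.** Staff review the diary with parents 7 days after each injection (Protocol 8.10.2). With the +3 day window in the Schedule of Assessments, that is Day 8 to 11 or Day 64 to 67. Part 1 adds reviews on Days 4 and 60 (±1 day). No question about a 24-hour duration is specified at these contacts. SAP 6.3.2 computes duration in whole days, as end minus start plus one, whether or not the reaction was continuous, so it does not establish 24 hours at Grade 3+.

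**The case against.** The strongest reply is that footnote b only prompts a call; it does not define what counts. Rules 2 and 3 count any qualifying reaction, however it comes to light, and several other routes exist:

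- Investigators, the medical monitor and the Sponsor all watch for pause events, and the investigator must report a potential pause event within 24 hours of observing it (Protocol 7.4).
- An eDiary record that identifies a relevant safety event triggers a follow-up contact (8.10.2), and reactogenicity may prompt an unscheduled visit (Section 8).
- Changes in severity are to be documented so that time at each intensity can be assessed (8.11.7).
- Part 1, where two cases can suffice, also has the Day 4 and Day 60 visits and the internal safety team reviews.

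Much of this stands, and it rules out stronger readings. A reader might infer that duration is asked about only when entries are 22 hours or more apart; the missing-entry prompt shows otherwise. A reader might infer that any slightly earlier second entry escapes; the 22-hour limit already tolerates 2 hours. A reader might infer that unprompted reactions are not counted; nothing in Table 4 excludes them.

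What the reply does not do is close the gap. None of these routes specifies asking whether a Grade 3 reaction lasted 24 hours, the reporting duty begins only once someone has observed the event, and the scheduled reviews mostly come later. The safety board and internal safety team charters might add detail, but they are not among the documents.

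**Conclusion.** The point holds as a mismatch between the tracking footnote and the criterion it serves. Consecutive-day Grade 3+ entries less than 22 hours apart fall outside both prompts, although the reaction may meet the duration criterion. The likely consequence is delayed recognition, and possibly missed recognition, of two-day Grade 3 reactions. This matters most in arms of 40 or fewer; at 300 participants, where 15 cases are needed, the harm is mainly delay.

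The size is uncertain. The 0.2% to 24% of pairs rests on an assumed entry-time SD of 0.5 to 2 hours, independence and normality. The 0.5% to 42% further assumes exactly two cases, each lasting two diary days. A reader might take these as rates of missed pause events. They are not: they describe only the absence of a prompt under footnote b, before any other route is considered. Nor is this an error in the pause thresholds. It is a modest procedural gap, worth closing because the rule protects infants and the change is small.

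**What to change.** Reconcile footnote b with the duration criterion in rules 2 and 3, so that Grade 3+ entries of the same reaction for two consecutive diary days prompt the duration question regardless of the clock interval between them. Replace the malformed hour range. Leave the missing-entry call and the Table 4 events and thresholds unchanged.

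The cost is one sentence in the footnote, one eDiary alert setting, and a few extra calls to parents who have already reported a Grade 3 or higher reaction.

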7.5. Lost to Follow-up

A participant will be considered LTFU if the participant's parent(s)/LAR(s) repeatedly fail to return for scheduled visits without stating an intention to withdraw consent and is unable to be contacted by the study site. The following actions must be taken if a participant fails to return to the clinic for a required study visit:

- The study site staff must attempt to contact the participant's parent(s)/LAR(s) and reschedule the missed visit as soon as possible, counsel the participant's parent(s)/LAR(s) on the importance of maintaining the assigned visit schedule and ascertain whether they wish the participant to and/or should continue in the study.
- Before a participant is deemed LTFU, the investigator or designee must make every effort to regain contact with the participant's parent(s)/LAR(s) (where possible, 3 telephone calls and, if necessary, a certified letter to the participant's last known mailing address or local equivalent methods). These contact attempts (eg, dates of telephone calls and registered letters) should be documented in the participant's medical record.
- A participant whose parent(s)/LAR(s) continue to be unreachable or continue to be noncompliant with study visits or procedures will be considered to have withdrawn from the study.
- A participant should not be considered LTFU until due diligence has been completed.

Protocol: mRNA-1273-P206, Original

8. STUDY ASSESSMENTS AND PROCEDURES

Participants will undergo study procedures at the time points specified in the SoA (Table 1).

A participant can also be seen for an unscheduled visit at any time during the study. An unscheduled visit may be prompted by reactogenicity issues, illness visit criteria for COVID-19, or new or ongoing AEs. The study site also has the discretion to make reminder telephone calls or send text messages to inform the participant's parent(s)/LAR(s) about visits, review eDiary requirements, or follow-up on ongoing or outstanding issues.

In accordance with FDA guidance on "Conduct of Clinical Trials of Medical Products During COVID-19 Public Health Emergency" (DHHS 2020), investigators may convert study site visits to home visits or telemedicine visits (with the exception of Screening, Day 1, Day 57, Day 85, Day 237, and Day 422) with the approval of the Sponsor (home visits also require site IRB approval). Such action should be taken to protect the safety and well-being of study participants and study site staff or to comply with state or municipal mandates.

